Adverse Event Assessment and Serious Adverse Events (SAE)	Continuously assessed using NCI CTCAE v.5		
Non-serious AEs will be collected starting with the first dose of the study drug and through 100 days after discontinuation of dosing.
 
All SAEs must be collected which occur within 100 days of discontinuation of dosing or completion of the participant's participation in the study if the last scheduled visit occurs at a later time, except in cases where a study participant has started a new anti-neoplastic therapy. However, any SAE occurring after the start of a new treatment that is suspected to be related to study treatment by the investigator will be reported. See Section 9.2.
 
All AEs (SAEs and non-serious AEs) associated with confirmed or suspected SARS-CoV-2 infection will be followed until resolution, the condition stabilizes, or is deemed irreversible, or until the participant is lost to follow-up (as defined in Section 8.3). For suspected cases, participants should be followed until SARS-CoV-2 infection is ruled out as per institutional policy on SARS-CoV-2.
 
COVID-19 or positive SARS-CoV-2 test results should be reported to BMS within 24 hours regardless of the seriousness criteria.

Assessment of post-SC injection reaction		X	
Parts A-D: Perform on Day 2 of each cycle of SC treatment.
 
Part E: Participants are contacted approximately 24 hours after the first 2 SC manual injections for reporting of any injection-site reactions.
 
See Section 9.4.7.

Table 2-3: On-treatment Procedural Outline (CA2098KX) - Parts A-E

Procedure	Parts A-D: Day 1 of each treatment cycle (Cycle = 28 days) Part E: [REDACTED] of each treatment cycle ^a (Cycle = 28 days)	Timepoints Relative to Dosing Schedule	Notes ^b
Laboratory Tests			
Parts A-D
 
Cycle 1 and Cycle 2: The laboratory tests may be performed within 48 hours prior to the first and second doses in the study.
 
Cycle 3 and beyond: The laboratory tests may be performed within 72 hours prior to dosing.
 
Pregnancy testing must be performed within 24 hours prior to dosing.
 
Part E
 
Perform on site/local laboratory testing within 72 hours prior to each dose.
 
For the first treatment visit, labs need not be repeated if they were performed within 72 hours and the results are available and have been reviewed for eligibility.
 
Refer to Section 9.4.4 for the list of laboratory tests to be conducted.

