In Part C and Part D, 1200 mg SC nivolumab (BMS-986298) + rHuPH20 (rHuPH20 concentration of 2,000 U/mL), should be administered via manual injection in one of the quadrants of the abdomen or, alternatively, in the thigh as steadily as possible (ie, no start or stop, and at a steady rate) over a period of approximately 3-5 minutes. Participants will be monitored for approximately 60 minutes following first manual injection of 1200 mg SC nivolumab + rHuPH20. Participants receiving subsequent SC injections may be monitored for approximately 15-30 minutes post injection at the discretion of the investigator. The site of SC injection, duration and needle type must be recorded in the electronic case report form (eCRF). Instructions for preparation of the SC nivolumab (BMS-986298) dose are provided in the Pharmacy Manual.

Protocol Amendment 04

In Part E, 600 mg SC nivolumab (BMS-986298) coformulated with rHuPH20 10,000 units (2000 Units/mL) should be administered on [REDACTED] of each treatment cycle, via manual injection in one of the quadrants of the abdomen or, alternatively, in the thigh as steadily as possible (ie, no start or stop, and at a steady rate) over a period of approximately 2-5 minutes. Participants will be evaluated for approximately 30 minutes post [REDACTED] SC injections. In addition, all participants will be contacted approximately 24 hours after the [REDACTED] SC injection and [REDACTED] SC injection for reporting of any injection-site reactions. The site of SC injection, duration, and needle type must be recorded in the electronic case report form (eCRF).

For Parts A-D, SC nivolumab and rHuPH20 were mixed at the site pharmacy (coadministration) prior to study drug administration. As of Protocol Amendment 04, coformulated drug product (SC nivolumab and rHuPH20 solutions pre-mixed in 1 vial with the same dose ratio) will be introduced for Part E. In addition, all ongoing participants in Parts C & D may switch to the coformulated drug product.

Instructions for preparation of the SC nivolumab (BMS-986298) coformulation dose are provided in the Pharmacy Manual.

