9.4 *Safety*

Planned time points for all safety assessments are listed in the Schedule of Activities ([Section 2](#)).

9.4.1 *Physical Examinations*

Refer to Schedule of Activities (Section 2).

9.4.2 *Vital signs*

Refer to Schedule of Activities (Section 2).

9.4.3 *Electrocardiograms*

Refer to Schedule of Activities (Section 2).

9.4.4 *Clinical Safety Laboratory Assessments*

Investigators must document their review of each laboratory safety report.

All clinical safety laboratory assessments will be performed locally per the Schedule of Activities (Section 2).

A central/local laboratory will perform the analyses and will provide reference ranges for these tests. Results of clinical laboratory tests performed on Day -1 must be available prior to dosing.

[Table 9.8-1](#) and [Table 9.8-2](#) list other various serologic tumor markers, gene mutation status, and genomic analyses.

Table 9.4.4-1: Laboratory Assessment Panels

Hematology - Complete Blood Count (CBC)	
Hemoglobin	
Hematocrit	
Total leukocyte count, including differential	
Platelet count	
Chemistry	
Aspartate aminotransferase (AST)	Albumin - screening only
Alanine aminotransferase (ALT)	Sodium
Total bilirubin	Potassium
Alkaline phosphatase (ALP)	Chloride
Lactate dehydrogenase (LDH)	Calcium
Creatinine	Phosphorus
Blood urea nitrogen (BUN) or serum urea	TSH, free T3, and free T4 - screening
Fasting glucose	TSH, with reflexive fT3 and fT4 if TSH is abnormal - on treatment
Serum alpha-fetoprotein (HCC only)	
Serology (at screening)	
Hepatitis B/C (HBV sAG, HCV antibody, or HCV RNA)	
Testing for HIV-1 and HIV-2 must be performed at sites where mandated by local requirements (see Appendix 8).	
Coagulation Panel (HCC only)	
PT/INR	
aPTT	
Fibrinogen	
Other Analyses	
Pregnancy test (WOCBP only: minimum sensitivity 25 IU/L or equivalent units of HCG).	
Follicle stimulating hormone (FSH) screening (only required to confirm menopause in women aged < 55 years)	

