9.4.5 Suicidal Risk Monitoring

Not applicable.

9.4.6 *Imaging Safety Assessment*

Any incidental findings of potential clinical relevance that are not directly associated with the objectives of the protocol should be evaluated and handled by the Study Investigator as per standard medical/clinical judgment.

9.4.7 *Assessment of Subcutaneous Injection Site*

The Investigator or designated study staff will assess the proposed injection site for signs of local irritation and inflammation. The proposed injection site will be evaluated prior to all SC doses and approximately 60 minutes after the Cycle 1 Day 1 injection (Parts A, B and D) and following the first SC injection after transitioning to 1200 mg dose in Part C. Part E participants will be monitored for approximately 30 minutes following the [REDACTED] and [REDACTED] SC manual injections. Participants receiving subsequent SC injections may be monitored post injection as clinically warranted and at the discretion of the investigator. There will be five pre-specified injection site reactions of interest: injection site erythema; injection site pain, injection site pruritus, injection site hematoma, and injection site swelling. Injection site reactions will be recorded as AEs on the appropriate page of the CRF. In addition, all participants will be contacted approximately 24 hours after the first 2 SC injections for reporting of injection site reactions. The injection site will also be evaluated predose at the next dosing visit.

9.5 *Pharmacokinetics*

Full details on the clinical pharmacology aspects of nivolumab can be found in the nivolumab IB.

The PK of nivolumab (BMS-936558 and BMS-986298) will be derived from serum concentration versus time measurements. The PK parameters to be assessed include:

- Cmax: Maximum observed serum nivolumab concentration
- Tmax: Time to maximal concentration
- AUC(TAU): Area under the concentration-time curve over the dosing interval
- Ctau: Observed serum nivolumab concentration at the end of the dosing interval
- Ctrough: Trough observed serum nivolumab concentration

Individual participant PK parameter values will be derived by non-compartmental and, if appropriate, population PK methods by a validated pharmacokinetic analysis program. Actual times of collection will be used in all PK analyses.

9.5.1 *Pharmacokinetics and Anti-drug Antibody Sample Collection and Processing*

[REDACTED]

[figure not shown]

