10.3.2 Safety Analyses

Safety analyses will be performed on the All Treated Participants population. Descriptive statistics of safety will be presented using NCI CTCAE v.5 by treatment group.

Endpoint	Statistical Analysis Methods
Incidence of AEs, TRAEs, SAEs, TRSAEs, AEs/TRAEs leading to discontinuation, and deaths	All on-study AEs, TRAEs, SAEs, TRSAEs, and AEs/ TRAEs leading to discontinuation will be tabulated using worst grade per NCI CTCAE v.5 criteria by system organ class and preferred term. Frequency distribution of treated participants with AE using the worst CTC grade. Participants will only be counted: (1) once at the PT level, (2) once at the SOC level, and (3) once in the “total participant” row at their worst CTC grade, regardless of SOC or PT. Deaths will be summarized by treatment group.
Incidence of clinical laboratory test abnormalities	On study laboratory parameters including hematology, chemistry, liver function, and renal function will be summarized using worst grade NCI CTCAE v.5 criteria.
Incidence of AEs in the MedDRA Anaphylactic Reaction broad scope SMQ occurring within 2 days after study drug administration	Descriptive statistics will be presented using NCI CTCAE v.5 criteria by treatment group.
Incidence of events within the hypersensitivity/infusion reaction select AE category occurring within 2 days after any study drug administration	Descriptive statistics will be presented using NCI CTCAE v.5 criteria by treatment group.

Abbreviations: AE = adverse event; CTC = Common Terminology Criteria; MedDRA = Medical Dictionary for Regulatory Activities; NCI CTCAE v5 = National Cancer Institute Common Terminology Criteria for Adverse Events version 5; PT = preferred term; SAE = serious adverse event; SMQ = standardized MedDRA query; SOC = system organ class; TRAE = treatment-related adverse event; TRSAE = treatment-related serious adverse event.

10.3.3 *Pharmacokinetic Analyses*

Pharmacokinetic analyses will be conducted using non-compartmental analysis and, if appropriate, PPK analysis. These analyses will be used to characterize the PK of SC nivolumab in Part A, Part B, Part D, and Part E, as well as to inform future clinical trials using SC nivolumab. Analyses from Part A and Part B were used to inform dose selection for Part C, Part D, and additional treatment groups in Part B.

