10.3.8 Interim Analyses

PK and safety analyses will be performed in the study on an ongoing basis. Interim analyses will be conducted in this study to select the SC nivolumab (BMS-986298) dose for Part C and for long-term dosing in Part D, and to inform additional dosing regimens to be assessed in Part B. Interim analysis are planned also for Parts C, D, and E as specified below. Details regarding interim analyses can be found in the Statistical Analysis Plan.

The following will be considered as part of determination of the SC dose:

- Interim analysis 1 included the first █ participants in Part A after single dose of subcutaneous nivolumab. Participants in Part A - Group 1 were analyzed.
- Interim analysis 2 occurred when all participants in Part B Group 3 had completed the single dose of subcutaneous nivolumab. Participants in Part A - Group 1 and Part B - Group 3 were analyzed.

Data from at least █ participants from Part A and from additional participants from Part B, were used to identify the SC nivolumab (BMS-986298) dose regimen in Part C and Part D of this study.

Based on preliminary PK results from Part A and Part B, SC dose of 1200 mg Q4W nivolumab is selected for Part C and Part D participants.

Interim analysis 3 will occur when the first 10 participants in Part D have completed the single dose of subcutaneous nivolumab. All participants enrolled in all Parts of the study up to the lock will be analyzed.

Interim analysis 4 will occur when all participants in Part D have completed the single dose of subcutaneous nivolumab. All participants enrolled in all Parts of the study up to the lock will be analyzed.

Interim analysis 5 will occur when all participants in Part E have completed a minimum of 6 months of follow-up from first dose date. All participants enrolled in all Parts of the study up to the lock will be analyzed.

Additional analysis for internal decision making or external publication purposes may be performed. No formal comparisons or inferences requiring any adjustment to statistical significance level will be performed.

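### Injection-site reactions are checked the day after every SC injection in Part D but only after the first two in Part E, so whole-period rates for the two parts are not like for like; the Section 9.4.7 contact sentence also needs limiting to Part E

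*Combined protocol and SAP*

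**What the plan says.** Table 2-3 sets two schedules for the post-injection reaction assessment. For the earlier parts: "Parts A-D: Perform on Day 2 of each cycle of SC treatment". For Part E: "Part E: Participants are contacted approximately 24 hours after the first 2 SC manual injections for reporting of any injection-site reactions". Parts C and D have one SC injection per 28-day cycle, so the first rule covers each of their injections.

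Table 2-3 refers the reader to Section 9.4.7, which says that "all participants will be contacted approximately 24 hours after the first 2 SC injections for reporting of injection site reactions" and leaves post-injection monitoring after later injections to the investigator. The same section requires a site check before every SC dose and adds: "The injection site will also be evaluated predose at the next dosing visit". It names five injection-site reactions of interest: erythema, pain, pruritus, hematoma and swelling.

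Two other places bear on which text governs. Section 9.4 states: "Planned time points for all safety assessments are listed in the Schedule of Activities". Section 7.1.3 gives the 24-hour contact only in its Part E paragraph: "In addition, all participants will be contacted approximately 24 hours after the [REDACTED] SC injection".

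On analysis, Section 10.3.2 states: "Descriptive statistics of safety will be presented using NCI CTCAE v.5 by treatment group". On-study AEs are tabulated at worst grade, each participant being counted once per preferred term, once per system organ class and once in the total. The only 2-day windows there are for the anaphylactic reaction query and the hypersensitivity/infusion reaction category. On timing, Section 10.3.8 says: "Interim analysis 5 will occur when all participants in Part E have completed a minimum of 6 months of follow-up from first dose date". That analysis takes in participants from all parts.

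**The concern.** Section 3.3 identifies local injection-site reactions as a risk of the SC route not observed with IV dosing. Section 5.1 makes them part of AE collection, and the safety profile of SC nivolumab is a secondary objective. Parts D and E will both appear in by-group safety output at interim analysis 5.

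A participant who is asked after every injection has more opportunities to report a brief local reaction than one who is asked twice. Section 3.2.4.2 describes the injection-site reactions seen with rHuPH20 as mostly mild and transient. Such events can be gone by the next predose check, 2 weeks later in Part E and 4 weeks later in Part D. Part E also gives twice as many injections in the same time, which raises the chance of at least one reaction. From a whole-period count, a reader cannot separate tolerability from these two features.

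The wording of Section 9.4.7 is a smaller, separate matter. A site that reads it alone could stop the next-day check after the second SC injection in Parts C and D.

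**Working it through.** **Comparing the texts**

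- Groups 1-4 (Parts A and B): one SC dose, in Cycle 1. Both texts call for a next-day check, so there is no conflict.
- Parts C and D, first two SC injections: both texts call for a check.
- Parts C and D, third SC injection on: Table 2-3 requires a Day 2 check; Section 9.4.7 requires no next-day contact.
- Part E: both texts give the first two injections only.

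The 9.4.7 sentence is introduced as an addition and does not say that contact is confined to those two injections. A site that follows Table 2-3 therefore also satisfies 9.4.7. Section 9.4 points to the Schedule of Activities for timing. Section 7.1.3 suggests that Part E wording was carried into 9.4.7 without its restriction.

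**Counting next-day checks under Table 2-3**

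Inputs: Part D every 4 weeks, Part E every 2 weeks, maximum 104 weeks. The plan gives no figure of its own to reproduce.

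- 24 weeks, close to the 6-month minimum for interim analysis 5: Part D 24/4 = 6 injections, 6 checked (100%); Part E 24/2 = 12 injections, 2 checked (2/12 = 17%).
- 104 weeks: Part D 104/4 = 26, 26 checked (100%); Part E 104/2 = 52, 2 checked (2/52 = 4%).

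**Illustration with assumed rates**

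The documents give no injection-site reaction rate. Assume a per-injection probability *p*, the same in both parts and independent between injections, and let *s* be the fraction of reactions at unasked Part E injections that are still recorded. Over 24 weeks, the share of participants with at least one recorded reaction is:

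- Part D: 1 − (1 − p)^6
- Part E: 1 − (1 − p)^2 × (1 − p·s)^10, where 10 = 12 − 2
- First two injections, either part: 1 − (1 − p)^2

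| p | Part D | Part E, s = 0 | Part E, s = 0.5 | Part E, s = 1 | First two, both parts |
|---|---|---|---|---|---|
| 2% | 11.4% | 4.0% | 13.1% | 21.5% | 4.0% |
| 5% | 26.5% | 9.8% | 29.9% | 46.0% | 9.8% |
| 10% | 46.9% | 19.0% | 51.5% | 71.8% | 19.0% |

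The whole-period rates are equal when (1 − p·s)^10 = (1 − p)^4, that is s = [1 − (1 − p)^0.4]/p. At p = 5% this is (1 − 0.9797)/0.05 ≈ 0.41. Below that value Part E looks better than Part D, and above it worse, with the same true risk per injection. The column s = 0 is an extreme, because predose checks and continuous AE collection will capture some unasked reactions.

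**The case against.** The case against has several parts, and much of it stands.

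The 9.4.7 sentence sets a floor, and Section 9.4 sends timing to Section 2, so this is an ambiguity that Table 2-3 most likely settles. A reader might infer a direct contradiction reaching everyone in Parts C and D. The documents do not support that. It can matter only from the third SC injection and only for participants still on SC treatment, and their number is not stated.

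No Part D versus Part E comparison is planned. Section 10.3.8 rules out formal comparisons needing adjustment, and injection-site reactions are not a separate endpoint in Table 4-1. Dose, interval and formulation differ as well. This limits the point to how descriptive rates are read.

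Part E has an in-person predose site check every 2 weeks, twice as often as Part D, and AEs are collected continuously in all parts. If reactions recur in the same people, a missed repeat changes no incidence row. A reader might infer that Part E will look falsely well tolerated; the illustration shows that the direction is not determined.

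Section 10.3 is a summary of a separate SAP that was not supplied, so a matched table may already exist. Its absence can be stated only for the protocol text.

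What remains is that the protocol's stated summary combines unequal asking with unequal injection numbers, and data already collected allow a better-matched count.

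**Conclusion.** The point holds as a modest matter of interpretation. Under Table 2-3, next-day solicitation covers 6 of 6 injections in Part D and 2 of 12 in Part E over 24 weeks. The whole-period, once-per-participant count in Section 10.3.2 does not allow for this or for the different number of injections. The schedule counts assume no delays or discontinuations. The size and direction of any distortion are unknown: the percentages above rest on assumed rates, independence between injections and an assumed recording fraction. A count over the first two injections removes the difference in injection number and gives both parts a scheduled next-day enquiry for each injection counted. The match is closer but not exact, since post-injection observation is about 60 minutes after the first dose in Part D and about 30 minutes in Part E. The 9.4.7 wording is a clarification. Neither matter touches the primary PK results or any error rate.

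**What to change.** 1. In Section 9.4.7, limit the two-injection contact sentence to Part E, and restate the Day 2 check in each SC cycle for Parts A-D.

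2. Unless the SAP already has it, add one descriptive table by treatment group and worst grade: number and percent of participants with any injection-site reaction, with the five pre-specified terms as sub-rows. Count the Cycle 1 dose for Groups 1-4 and the first two SC injections for Parts D and E. Show the first Part C injection separately, because those participants had already received an SC dose. Show later injections separately, with a footnote that Part E had no scheduled next-day contact after injection 2. State one fixed post-injection window for all groups; counting up to the next dose would give 2 weeks in Part E and 4 weeks in Part D. No text sets this window for injection-site reactions; the 2 days used elsewhere in Section 10.3.2 would serve.

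The cost is one wording change and one extra table from AE data already collected, with no added visits, participants or tests. Part D enrollment is complete, so the wording change affects only contacts for participants still on SC treatment. The contrast between Parts D and E stays descriptive, because dose, interval and formulation differ.

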9.8.1 Tumor Tissue Specimens

For Part A, the Cycle 1 Day 15 tumor biopsy is highly recommended but optional. For Part B and Part D, participants will be required to undergo on-treatment biopsy unless judged as posing unacceptable risk by the investigator. Sufficient, recent tumor tissue FFPE block from a metastatic tumor lesion or from an unresectable primary tumor lesion, which has not been previously irradiated, must be submitted. If a participant had a biopsy in the preceding 12 months, participants can be enrolled without needing a repeat biopsy after discussion with the Medical Monitor and availability of FFPE blocks [REDACTED] as delineated below. For Part E, screening and on-treatment tumor biopsies are highly recommended, but optional.

- 1) **Parts A-D only:** Pre-treatment tissue must be collected and locally confirmed for adequate tissue quantity and quality during the screening period prior to first dose of study treatment and then sent to the central laboratory for testing. Please refer to lab manual for detailed biopsy collection instructions. Up to 5 participants from each part of the trial (Part A and B) who do not meet tissue requirements may be allowed treatment after discussion with the Medical Monitor. Other exceptions may be provided at the discretion of the Medical Monitor.
 - a) Approximately 15 participants in Part D, who do not meet tissue requirements may be allowed treatment after discussion with the Medical Monitor.
 - b) Participants should not have received any systemic anticancer therapy after the date that the submitted tumor tissue was obtained. Exceptions may be made with Medical Monitor approval in cases where fresh tumor tissue or recent tumor tissue are inaccessible.
- 2) **Part E:** Tumor tissue collection is highly recommended, but optional. For all participants in Part E, including mUC participants, submission of an archival FFPE tissue block (preferred) or unstained slides of tumor tissue from core biopsy, excisional biopsy, or surgical specimen obtained within 12 months of enrollment is highly recommended.

- 3) The tumor tissue specimen must be a core biopsy, excisional biopsy, or surgical specimen. Fine needle biopsies, drainage of pleural effusions with cytospins, or punch biopsies are not considered adequate for biomarker review. Biopsies of bone lesions that do not have a soft tissue component or decalcified bone tumor samples are also not acceptable. Where possible, the biopsied lesion should be distinct from target lesions being evaluated for radiologic response, and the same lesion should be used for both the baseline and on-treatment sampling.

